7.3 Procedure for Reporting an Adverse Event

Adverse events will be documented during this study by completing the AE Form. During the visit, AEs will be evaluated by a member of the study staff. The nature of each event and date of onset, outcome, course, maximum intensity and action taken with respect to treatment should be established. Details of any corrective treatment should be recorded on the AE Form. Investigators should follow-up on the status of subjects experiencing an ongoing AE until the event has been resolved, or until the condition has stabilized.

7.3.1. The Investigator or designee will notify the Study Manager or Monitor within 24 hours of any Serious Adverse Event that occurred during the study. The sponsor will promptly review all information relevant to the safety of the investigational device.

7.3.2. The investigator or designee must notify the sponsor and reviewing IRB by phone or fax of Unanticipated Serious Device-Related Adverse Events within 24 hours of learning of the event, followed by a written report within 10 working days after learning of the event.

7.3.3. Upon receipt of a report of an UADE by the Ascensia Study Manager or Monitor, the report will be immediately forwarded to:

[name] Ascensia Director of Medical and Scientific Affairs [REDACTED] [REDACTED] [REDACTED] [REDACTED]
--

7.3.4. The sponsor (Ascensia) must report UADEs to the FDA, all participating investigators, and reviewing IRBs within 10 working days after the sponsor first receives notice of the event.

7.3.5. Regardless of the above definitions, any additional adverse experience that the investigator considers serious, and/or of concern in relationship to the study must be documented and reported to the Study Manager or Monitor within 24 hours.

7.4 Medical Device Reporting

The Microlet NEXT lancing device system is an Ascensia-marketed product in the US. If an AE occurs that is directly caused by the marketed product, the AE should be reported immediately, but in any case within 24 hours, to the Customer Service Department at [name]. Also contact the Ascensia representative listed in Section 12.0.

8.0 Study Termination and Subject Withdrawal Criteria

8.1 Criteria to Withdraw / Discontinue a Subject from Study

Subjects may be withdrawn from the study at their own request for any reason, or at the discretion of the PI (or designee) for one of the following reasons:

- 1) Adverse Event
- 2) Illness of a subject
- 3) Subject non-compliance with protocol requirements
- 4) Other, at the discretion of the investigator

In such cases, the subject will be withdrawn from further study participation. Data collected from withdrawn subjects will be analyzed and results will be retained for safety assessments. If available, data will be retained in analyses related to the primary objective of the study unless there is a valid reason to believe that the data may be biased, incorrect, or confounded.

9.0 Regulatory

9.1 Regulatory Status of the Investigational Devices

In addition to the regulations outlined in the Ascensia Diabetes Care Global Clinical Affairs standard operating procedures, this protocol also complies with the clinical trial regulations of British Standard BS EN 13612:2002, "Performance evaluation of in vitro diagnostic medical devices."

9.2 Investigational Review Board (IRB) Approval

Prior to study initiation, an IRB must review this protocol, the ICF, and any other supporting study documents which impact subject safety. The investigational site may not begin the study until the IRB has given its written and dated approval via a letter that identifies the version/date of the protocol and ICF. A copy of the IRB approval letter and approved ICF must be provided to the Investigator and to Ascensia prior to the Study Initiation Visit.

9.3 Informed Consent Requirement

Each subject must provide informed consent before she/he can participate in the study. The informed consent process fully apprises the subjects of the risks and benefits to them and to society for participating in the study. The ICF will clearly state that designated study personnel will be able to view the subject's medical records. The ICF will also state that Ascensia representatives may observe some subjects as part of study staff training, study monitoring or for troubleshooting problems with the investigational devices.

If the subject understands and agrees to participate in the study, she/he will sign the ICF. All subjects will be given a copy of the ICF. If a subject has a question about his/her rights, he/she may contact a member of the IRB at any time during or after study participation.

9.4 Study Documentation Procedures

The investigator will keep study records for a minimum of three years. Alternatively, other arrangements may be made with Ascensia for study document storage.

9.5 Study Monitoring

The study will be monitored by Ascensia representatives. A monitoring plan will be completed by the Study Manager/designee prior to the study. The Study Manager or designee will conduct a study initiation visit, at least 1 monitoring visit, and a close-out visit. Note: the latter two visits may occur within a continuous timeframe.

Ascensia representatives may observe some subject visits as part of study monitoring. This will be done under supervision of the investigator. Ascensia representatives will maintain subject confidentiality and will not interfere with rights of human subjects, safety or bias study conduct.

9.6 Investigator's Report of Study Closure

Ascensia representatives will send a letter to the site informing them that the study is closed. The study will be considered closed when the data has been locked for data analysis.

The Investigator or designee will submit a report summarizing subject disposition and other study details, as appropriate, to the Ascensia Study Manager and the reviewing IRB. This report will be completed within 3 months of the study closure date.

In addition, the Ascensia Study Manager, or designee, will report the completion of the study to the IRB within 6 months of study closure.

9.7 Registration of Trial

The clinical trial will be registered with www.clinicaltrials.gov as required.

9.8 Clinical Study Reports (CSR)

Four CSRs will be written by the sponsor. Two CSRs will be written for CONTOUR NEXT: one report will evaluate data according to ISO 15197:2013 criteria and one report according to FDA SMBG:2016 criteria. Two CSRs will be written for CONTOUR TV3: one report will evaluate data according to ISO 15197:2013 criteria and one report according to FDA SMBG:2016 criteria.

10.0 Data Collection and Management

A unique number will identify each subject. The unique number will be the only identifying information entered. A master list of subject names, with their subject IDs, will be kept by the Investigator at the study site. The Investigator will retain all signed IC documents.

Clinical data will be primarily collected through an EDC system used by Ascensia. Study data will be recorded on forms that will serve as source documents for the EDC system. These original Forms will be retained by the site.

In addition to data collection, the EDC system will be used for data cleaning as well as monitoring operations. Site and sponsor users will be trained on the system prior to the study start, and their access to EDC system will be contingent upon successful completion of training requirements. Study personnel will complete and sign all appropriate source document forms in compliance with Good Clinical Practice (GCP). Source documents (Forms) should be completed legibly, in black or blue ink. If it is necessary to make corrections, a single line should be drawn through the original entry, the new entry written in, and the correction initialed and dated by the individual making the correction.

The original forms will be retained by the Investigator for a minimum of three years.

The Investigator or designee will sign and date an AE Form for each AE experienced by any subject.

YSI source documents (tapes) will be photocopied to preserve the image on the thermal paper. Site staff or designees who photocopy the YSI tapes will certify (with signature, date, and YSI ID) that the copy is a true and accurate representation of the original.

11.0 Data Analysis

The following analyses apply to both CONTOUR NEXT and CONTOUR TV3 meters, with analyses for each meter independent of the other.

11.1 Accuracy Objectives

Primary Objective – Accuracy with All Subjects Included

Let MeterBG = meter blood glucose result;

LabBG = laboratory method (YSI) comparator blood glucose result.

For the primary accuracy objective, a result (MeterBG) is considered accurate if:

$$|RD| = 100 * |MeterBG - LabBG| / LabBG \leq 15\%, \text{ regardless of the value of LabBG.}$$

With $n = 350$ evaluable results, $X_c = 333$ results would be required to satisfy the accuracy criteria. At $P_0 = 96.65\%$, there is approximately a 95% chance of satisfying the primary objective. Conversely, at $P_a = 92.81\%$, there is approximately a 95% chance of failing to satisfy this accuracy objective.

In addition to the $\pm 15\%$ accuracy definition, at least 99% of the $n = 350$ fingerstick results must satisfy:

$$|RD| = 100 * |MeterBG - LabBG| / LabBG \leq 20\%, \text{ regardless of the value of LabBG.}$$

Thus at least 347 out of $n = 350$ results must satisfy the $\pm 20\%$ accuracy definition.

With $n = 350$ evaluable results, $X_c = 347$ results would be required to satisfy the accuracy criteria. At $P_0 = 99.61\%$, there is approximately a 95% chance of satisfying this objective. Conversely, at $P_a = 97.80\%$, there is approximately a 95% chance of failing to satisfy this accuracy objective.

Secondary Objectives

Assume 315 evaluable results from people with diabetes. The ISO 15197:2013 acceptance criterion is that 95% of those evaluable results must satisfy the accuracy criteria:

$$|D| = |MeterBG - LabBG| \leq 15 \text{ mg/dL, for LabBG} < 100 \text{ mg/dL}$$

or

$$|RD| = 100 * |MeterBG - LabBG| / LabBG \leq 15\%, \text{ for LabBG} \geq 100 \text{ mg/dL.}$$

With $n = 315$, $X_c = 300$ results would be required to satisfy the accuracy criteria. At $P_0 = 96.79\%$, there is approximately a 95% chance of satisfying the primary objective. Conversely, at $P_a = 92.77\%$, there is approximately a 95% chance of failing to satisfy this objective.

Secondary Objective –Internal Requirements

1. $\pm 10.5\%$ or $\pm 10.5\text{mg/dL}$ (CONTOUR NEXT)

The hypothesis:

$$H_0: \Pr\{|\text{RD}| \leq 10.5\% \text{ when YSI} \geq 100\text{mg/dL or } |\text{D}| \leq 10.5\text{mg/dL when YSI} < 100\text{mg/dL}\} < 0.95$$

Will be tested against the alternative:

$$H_1: \Pr\{|\text{RD}| \leq 10.5\% \text{ when YSI} \geq 100\text{mg/dL or } |\text{D}| \leq 10.5\text{mg/dL when YSI} < 100\text{mg/dL}\} \geq 0.95$$

With $n = 315$, the critical number of “successes” is $X_c = 294$. That is, at least 294 out of $n = 315$ results must satisfy the requirement:

$$|\text{RD}| \leq 10.5\% \text{ when YSI} \geq 100\text{mg/dL or } |\text{D}| \leq 10.5\text{mg/dL when YSI} < 100\text{mg/dL}$$

This acceptance criterion (critical value) gives about a 92.62% chance of rejecting H_0 in favor of H_1 if the actual probability of “success” is 0.95.

2. $\pm 12.5\%$ or $\pm 12.5\text{mg/dL}$ (CONTOUR TV3)

The hypothesis:

$$H_0: \Pr\{|\text{RD}| \leq 12.5\% \text{ when YSI} \geq 100\text{mg/dL or } |\text{D}| \leq 12.5\text{mg/dL when YSI} < 100\text{mg/dL}\} < 0.95$$

Will be tested against the alternative:

$$H_1: \Pr\{|\text{RD}| \leq 12.5\% \text{ when YSI} \geq 100\text{mg/dL or } |\text{D}| \leq 12.5\text{mg/dL when YSI} < 100\text{mg/dL}\} \geq 0.95$$

With $n = 315$, the critical number of “successes” is $X_c = 294$. That is, at least 294 out of $n = 315$ results must satisfy the requirement:

$$|\text{RD}| \leq 12.5\% \text{ when YSI} \geq 100\text{mg/dL or } |\text{D}| \leq 12.5\text{mg/dL when YSI} < 100\text{mg/dL}$$

This acceptance criterion (critical value) gives about a 92.62% chance of rejecting H_0 in favor of H_1 if the actual probability of “success” is 0.95.

3. Study Staff Test

Two tests of the hypotheses will be performed.

The hypothesis:

$H_0: \Pr\{|\text{RD}| \leq 15\% \text{ when YSI} \geq 100\text{mg/dL} \text{ or } |\text{D}| \leq 15\text{mg/dL} \text{ when YSI} < 100\text{mg/dL}\} < 0.95$

will be tested against the alternative:

$H_1: \Pr\{|\text{RD}| \leq 15\% \text{ when YSI} \geq 100\text{mg/dL} \text{ or } |\text{D}| \leq 15\text{mg/dL} \text{ when YSI} < 100\text{mg/dL}\} \geq 0.95$

One test will be done using data from all subjects, and another using data only from PWD subjects. In the case of all subjects, if $n = 350$, the critical value is 327. For PWD subjects only, if $n = 315$, the critical value is 294. As in all cases, critical values may require adjustment due to differences in sample sizes. The critical values are chosen so that the least upper bound on the probability of passing under minimally acceptable conditions is 95%.

Table 11.1 summarizes critical values for satisfying objectives described in section 2. The column labeled P_o is the minimally acceptable condition (probability) for each objective listed.

Table 11.1 Sample Sizes and Critical Values for Satisfying Objectives

Objective	Sample Size, n	Critical Value, Xc	Po	Derivation of Critical Value*
2.1.1(95%), 2.2.1	350	333	96.65%	95% of n
2.1.1(9%)	350	347	99.61%	99% of n
2.3.1, 2.3.2, 2.3.3	315	300	96.79%	$\Pr\{\text{PASS} X_c, P_o\} \approx 95\%$
2.4.1	315	294	95.00%	$\Pr\{\text{PASS} X_c, P_o\} \approx 95\%$
2.4.2 (all subjects)	350	327	95.00%	$\Pr\{\text{PASS} X_c, P_o\} \approx 95\%$
2.4.2 (PWDs)	315	294	95.00%	$\Pr\{\text{PASS} X_c, P_o\} \approx 95\%$
2.2.2 (Questionnaire 1, All Subjects)	350	307	90.00%	$\Pr\{\text{PASS} X_c, P_o\} \approx 95\%$
2.3.4 (Questionnaire 1, PWDs)	315	276	90.00%	$\Pr\{\text{PASS} X_c, P_o\} \approx 95\%$
*Critical Values may change depending on actual sample size				

Note that error distribution tables will be constructed, to reflect the numbers and percentages of results falling within various error ranges (e.g., $\pm 5\%$, $\pm 7\%$, $\pm 10\%$, $\pm 12.5\%$, $\pm 15\%$, $\pm 20\%$). Tables will be by clinical site and overall.

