2.0 Study Objectives

Study objectives 2.1 and 2.2 are in accordance with **FDA SMBG: 2016**, Section C. Method Comparison / User Evaluation, and apply to data collected from **all subjects**: people with diabetes and a smaller number of naïve users (defined as people without diabetes). The objectives apply to both CONTOUR NEXT and CONTOUR TV3 BGMS, and the results from the two meter systems will not be compared to each other.

2.1 Primary Objective (FDA SMBG: 2016), all subjects:

2.1.1 Fingerstick Test: Obtain BGMS performance data in the hands of **lay users with diabetes and naïve users** (without diabetes) from fingerstick capillary blood using Microlet NEXT[®] lancing device.

- **95% of glucose results shall fall within $\pm 15\%$ of laboratory method across the entire tested range**
- **99% of glucose results shall fall within $\pm 20\%$ of laboratory method across the entire tested range**

2.1.2 Samples will adequately span the claimed measuring range. At least ten unaltered samples with blood glucose concentration at the lower limits of the measuring range (less than 80 mg/dl) and at least ten unaltered samples at the upper limit measuring range (greater than 250 mg/dl) will be obtained for each anatomical site (i.e. fingerstick & palm).

¹ Self-Monitoring Blood Glucose Test Systems for Over-the-Counter Use, Guidance for Industry and Food and Drug Administration Staff. Issued 11Oct2016, Food and Drug Administration, USA. (abbreviated FDA SMBG:2016)

² In vitro diagnostic test systems – Requirements for blood-glucose monitoring systems for self-testing in managing diabetes mellitus. Issued 15 May2013, International Organization for Standardization, Switzerland. (abbreviated ISO 15197:2013)

2.2 Secondary Objectives (FDA SMBG: 2016), all subjects:

- 2.2.1 Alternative Site Test (AST): Obtain BGMS performance data in the hands of **lay users with diabetes and naïve users** (without diabetes) from the palm site using the Microlet NEXT lancing device with the AST endcap. Acceptance criteria will be the same as fingerstick 2.1.1.

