3.0 Study Design Summary

This study was designed to satisfy both the *FDA SMBG:2016* and the *ISO 15197:2013, Section 8* requirements. Besides different analysis criteria, the main difference between these regulations is that FDA SMBG:2016 requires that both naïve users (people without diabetes) and people with diabetes are included in the study population. The ISO 15197:2013 standard states that the study population shall be people with diabetes.

The study will be conducted at two clinical sites and enroll a total of approximately 370 lay users. Ten to fifteen percent (10 - 15%) of the enrolled subjects will be people without diabetes and the remaining subjects will be people with diabetes.

For this study, there must be at least 350 total evaluable fingerstick self-test results and at least 350 total evaluable AST palm self-test results for each BGMS, CONTOUR NEXT and CONTOUR TV3. In addition, per FDA SMBG:2016, at least 10 unaltered fingerstick blood samples will be < 80 mg/dL and 10 will be > 250 mg/dL. Subject enrollment will continue until the required evaluable samples are collected.

Sites are not required to replace subjects with diabetes who did not have evaluable venous blood results.

The subjects will be 18 years and older. Each subject will make one visit, lasting approximately 2 hours, to the clinical trial site. Study sessions will be conducted by study staff members who have been trained on all aspects of the protocol, forms, the use of the CONTOUR NEXT and CONTOUR TV3 systems, data collection, and GCP.

All subjects will complete the informed consent process before performing any study procedures.

Procedures - All Subjects

According to a randomization schedule, subjects will be assigned to: 1) use either the CONTOUR NEXT or CONTOUR TV3 meter first, and 2) use one of three test strip lots corresponding to each meter throughout the visit.

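### Section 11.1 gives about a 95% chance of meeting the primary objective, but that counts only the ±15% criterion; with the required ±20% criterion it is about 91% at the plan's own rates

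*Combined protocol and SAP*

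**What the plan says.** Section 2.1.1 puts two acceptance criteria under the primary objective: "95% of glucose results shall fall within" ±15% of the laboratory method, and "99% of glucose results shall fall within" ±20%. Section 3.0 requires "at least 350 total evaluable fingerstick self-test results" for each meter.

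Section 11.1 treats the criteria one after the other. For ±15% it sets 333 of 350 as the critical value and states that, at P0 = 96.65%, "there is approximately a 95% chance of satisfying the primary objective". It then makes the ±20% criterion an additional requirement, with 347 of 350 as the critical value, and states that at P0 = 99.61% "there is approximately a 95% chance of satisfying this objective". Matching Pa values (92.81% and 97.80%) are given for a 95% chance of failing each criterion.

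Table 11.1 lists the two parts of 2.1.1 on separate rows, and section 11.1 describes its Po column as the minimally acceptable condition. Neither place gives the chance of meeting both criteria. Palm objective 2.2.1 adopts the acceptance criteria of 2.1.1, but Table 11.1 lists it only on the 333 row, at Po = 96.65%.

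**The concern.** The sentence names the whole primary objective, but the calculation behind it covers only one of the two criteria. A meter can pass ±15% and still fail ±20%, so the ±15% figure is only an upper bound on the chance of passing. The bound is close only if the ±20% criterion almost never fails, and the plan itself gives that criterion a 5% failure chance at its P0.

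A ±15% rate also cannot determine the answer by itself. The ±20% criterion depends on the tail of the error distribution, and one value of the ±15% rate is compatible with many tails.

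What is at stake is the stated operating characteristic of the primary endpoint, for each of two meters. Anyone using section 11.1 to judge the risk that an acceptable meter fails would read 5%, and the plan's own inputs give nearly twice that.

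**Working it through.** **Inputs** (sections 2.1.1, 3.0 and 11.1)
- n = 350 evaluable fingerstick results per meter.
- ±15% criterion: at least 333 within, so at most 17 outside. P0 = 0.9665.
- ±20% criterion: at least 347 within, so at most 3 outside. P0 = 0.9961.
- Assumption: results from different subjects are independent, as the plan's own binomial figures also require.

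**Step 1. Reproduce the plan's figures (exact binomial).**
- P(X ≥ 333 | 350, 0.9665) = 0.9500
- P(X ≥ 347 | 350, 0.9961) = 0.9505
- Chance of failing at Pa: 0.9495 for ±15% at 92.81%, and 0.9500 for ±20% at 97.80%.

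All four match section 11.1.

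**Step 2. Chance of meeting both.** Any result outside ±20% is also outside ±15%, so each result falls in one of three classes:
- within ±15%: 0.9665
- between ±15% and ±20%: 0.9961 − 0.9665 = 0.0296
- beyond ±20%: 1 − 0.9961 = 0.0039

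Let k be the number beyond ±20%. Given k, each of the other 350 − k results lies between ±15% and ±20% with probability 0.0296 / 0.9961 = 0.02972, and at most 17 − k of them may do so:

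P(both) = Σ over k = 0 to 3 of Bin(k; 350, 0.0039) × P(Bin(350 − k, 0.02972) ≤ 17 − k)

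| k | P(k beyond ±20%) | P(at most 17 − k between) | Product |
|---|---|---|---|
| 0 | 0.2547 | 0.9815 | 0.2500 |
| 1 | 0.3490 | 0.9662 | 0.3372 |
| 2 | 0.2385 | 0.9412 | 0.2244 |
| 3 | 0.1083 | 0.9026 | 0.0978 |
| **Sum** | | | **0.909** |

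Unrounded, the sum is 0.9094. A simulation of 1,000,000 trials gives 0.9096. As a check, the answer must lie between 0.9500 + 0.9505 − 1 = 0.9005 and 0.9500. The failure risk is 1 − 0.909 = 9.1%.

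**Step 3. Dependence on the tail, with the ±15% rate held at 96.65%.** The rates in the first, third and fourth rows, and the error models in the last two, are assumptions.

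| Tail | Within ±20% | P(both) |
|---|---|---|
| Rate set directly | 99.5% | 0.866 |
| Plan's P0 | 99.61% | 0.909 |
| Rate set directly | 99.7% | 0.932 |
| Rate set directly | 99.9% | 0.950 |
| Normal errors, zero bias, SD 7.06% | 99.54% | 0.884 |
| Scaled t errors, 10 df, zero bias | 99.18% | 0.66 |

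**Step 4. Rates that give a joint 95%.** Multiply both failure rates by 0.888: 0.0335 × 0.888 = 0.0297 and 0.0039 × 0.888 = 0.0035. At about 97.03% and 99.65%, P(both) = 0.95. Other pairs also give 95%.

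**Step 5. At the two Pa values together** (92.81% and 97.80%), P(both) = 0.013. A poor meter is passed less often than either single-criterion figure suggests.

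**The case against.** The strongest reply is that this is loose wording and not an arithmetic error. Every figure in section 11.1 reproduces. The 95% sentence follows directly on the ±15% definition and the 333 critical value, the ±20% criterion has its own P0 and Pa, and Table 11.1 separates the two. The same phrase about the primary objective recurs in the n = 315 paragraph on a secondary objective, which suggests carried-over text. It stands that the per-criterion arithmetic is right and that the fault lies in the label and the missing joint figure. The label still names an objective that section 2.1.1 defines by both criteria.

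A second reply is that the plan never says its two P0 values hold together, and that they are boundary values, not expected performance. This also stands in part. The 91% is conditional on that pair, and 9.1% is the failure risk of a minimally acceptable meter, not a forecast. Slightly better meters do well: with zero-bias normal errors, an SD of 6.8% gives 0.964 and an SD of 6.5% gives 0.993. But no other pair of rates is offered, and at a ±15% rate of 96.65% the joint chance reaches 95% only if the ±20% criterion is almost certain to be met.

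A third reply is that nothing operational changes and that the error concerns only the sponsor's risk of failing an acceptable meter. That is true and limits the consequences. It does not make the stated probability correct.

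For palm, section 11.1 has no sentence of its own giving a 95% chance. However, Table 11.1 puts objective 2.2.1 at the same Po, and section 11.1 ties the minimally acceptable condition to a 95% passing probability, so the same correction applies there.

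**Conclusion.** The concern holds. The chance stated for the primary objective is the chance for its ±15% criterion alone. At the plan's own pair of rates, 96.65% and 99.61%, the chance of meeting both criteria is 0.909, which is 4.1 percentage points below the stated 95%. The failure risk is 9.1% instead of 5%. This rests on independent results across subjects, n = 350, and both rates holding together; no correlation between the criteria has to be assumed. With zero-bias normal errors fitted to the ±15% rate, the joint chance is 0.884. The figures apply to each meter separately, and to palm testing under 2.2.1 at the same n and rates. The risk of passing a poor meter is not understated, and no critical value or pass/fail decision is affected. The correction should be made because the figure describes the primary endpoint.

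**What to change.** In section 11.1, attach the first P0/Pa pair to the ±15% criterion and the second to the ±20% criterion, and keep the term primary objective for meeting both. Then add a sentence such as: *At true rates of 96.65% within ±15% and 99.61% within ±20%, the chance of meeting both criteria with n = 350 is about 91%; a chance of about 95% requires roughly 97.03% and 99.65%.* State that this assumes independent results across subjects and depends on the tail of the error distribution.

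Add a note to Table 11.1 that the Po values for 2.1.1 apply to one criterion each, and that 2.2.1 is subject to both.

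The cost is two sentences and a table note. The sample size, both critical values and the acceptance criteria do not change. The stated chance of passing becomes somewhat less favourable.
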